11.2 Analysis Populations

- The Intent to Treat (ITT) population consists of all randomized patients.
- The As Treated (AT) population is the subset of the ITT population consisting of all patients for whom the index procedure is begun, whether or not the index procedure is completed. If multiple procedures were attempted, the last procedure with the study valve deployed will be considered the index procedure and used for determining the As Treated trial arm assignment and the date of the index procedure will be used for determining all follow-up visits and related assessment. A randomized TAVR patient for whom the TAVR procedure is never started will not be part of the AT population, even if that patient should receive a SAVR implant.
- The Valve Implant (VI) population is the subset of the AT population consisting of all patients who receive and retain the intended valve during the index procedure. Patients who receive a valve in valve implant will be part of the VI population. Patients who are converted from TAVR to SAVR during the procedure will not be part of the VI population.

The AT population will be the primary population for trial endpoint analysis. The VI population will be used for analysis of echo data and related endpoints. Selected sensitivity analyses will be performed using the ITT population.

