8.3 Procedure (Day 0)

The valve implant procedure should occur within 14 days of randomization and no later than 30 days after informed consent is obtained. The date of the valve implant procedure is considered Day 0. The valve implant procedure will be considered to have started when:

- The first interventional access related puncture (venous or arterial) is established for TAVR.
- The first skin incision is performed for SAVR.

Performance of TEE does not by itself constitute start of procedure.

For those patients receiving TAVR, the commercially available SAPIEN 3 THV with the Commander Delivery System, or the Certitude Delivery system if treated with a transapical or transaortic approach as part of the Alternative Access registry [enrollment closed], and components will be used per the most current Instructions for Use (IFU) at all times for device sizing, preparation, and recommended implant

procedure. Refer to Appendix C for the IFUs to be used in this study.

For those patients receiving SAVR, a commercially available bioprosthetic surgical valve and associated components will be used according to institution standard of care.

Day 0 will be used to schedule all subsequent visits and calculate visit windows. Patients who receive the assigned TAVR or SAVR implant will continue in the study and complete the study through year 10 according to the visits and events described in section 8.0 and Schedule of Procedures.

Day 0 valve implant procedure assessments will include the following:

Systems:

- Medications including all antithrombotics/anticoagulants and HMG coA reductase inhibitors.
- Adverse event assessment

Cardiopulmonary:

- Comprehensive transthoracic (TTE) or transesophageal (TEE) echocardiogram
- Supra-aortic angiogram or TEE

If the valve implant is aborted (prior to or after the start of the valve implant procedure), the Day 0 visit may be re-scheduled if the patient continues to meet all inclusion/exclusion criteria.

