11.3 Timing

- The index procedure date is defined as Day 0. For randomized patients who do not have the procedure attempted, the randomization date will be used as Day 0.
- Time intervals for events will be computed by subtracting the event date minus day 0. For example, if the procedure occurs on January 1, and the patient dies on January 31, the death will be considered a 30 day death for analysis.
- The timing for all visits will be based on the index procedure date. If the patient never receives the procedure the 30-day visit will never be due; later visits for such patients will be based on the randomization date.
- In analysis of time-dependent variables, one year is defined as 365.25 days, and one month as 30.4375 (= 365.25/12) days.

For information depending on follow-up windows any visit within the specified window will be used, without regard to the actual timing of the visit.

- Analysis close date:
 - The analysis close date for the initial analysis will be the earlier of the following two dates: One year past the last index procedure
 - One year plus 60 days past the last randomization. This condition is in order to account for a potential patient with a severely delayed procedure.
- The analysis close date for later reports will be determined prior to the report. Unless otherwise specified such dates will be at annual intervals past the initial analysis close date.
- All database information will be used to determine patient survival as of the analysis close date.
- Adverse events occurring after the relevant analysis close date will not be included in adverse event analysis.
- Information dependent on a visit window, such as echo or NYHA, will be included in analysis as long as the window starts on or before the analysis close date.

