Endocarditis	
Endocarditis must meet at least 1 of the following criteria:
 
 1. Patient has organisms cultured from valve or vegetation 2. Patient has 2 or more of the following signs or symptoms: 
 • Fever (>38°C) • New or changing murmur • Embolic phenomena • Skin manifestations (i.e., petechiae, splinter hemorrhages, painful subcutaneous nodules) • CHF • Cardiac conduction abnormality 
With no other recognized cause and at least 1 of the following:
 
 a. organisms cultured from 2 or more blood cultures b. organisms seen on Gram's stain of valve when culture is negative or not done c. valvular vegetation seen during an invasive procedure or autopsy d. positive laboratory test on blood or urine (e.g., antigen tests for H influenzae, S pneumoniae, N meningitidis, or Group B Streptococcus) e. evidence of new vegetation seen on echocardiogram and if diagnosis is made antemortem, physician institutes appropriate antimicrobial therapy. Infection of the endocardial surface of the heart which may include one or more heart valves, the mural endocardium, or a septal defect 	STS
EuroSCORE II	http://www.euroscore.org/calc.html	European System for Cardiac Operative Risk Evaluation
EuroSCORE, logistic	http://www.euroscore.org/calcold.html	European System for Cardiac Operative Risk Evaluation
Explant	Removal of the investigational valve implant for any reason	Sponsor

Term	Definition	Reference/ Justification
Hemolysis	Evidence of RBC destruction best explained by hemolysis (LDH >350 u/L and decreased haptoglobin based on site lab normals) and no other explanation for the findings. Microscopic evidence may be considered supportive.	Sponsor
Hospitalization (repeat)	Any unplanned admission to the hospital (including an emergency department visit) for either a diagnostic or therapeutic purpose (e.g. diuretics, inotropes, chronotropes, oral or intra-venous therapy) following discharge from the index hospitalization	Sponsor

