Hospitalization for CHF	An event where the patient is admitted to the hospital with a primary diagnosis of CHF where the length of stay is at least 24 h (or extends over a calendar date if the hospital admission and discharge times are unavailable), and the patient exhibits new or worsening symptoms of CHF on presentation, has objective evidence of new or worsening CHF, and receives initiation or intensification of treatment specifically for CHF. Clinical symptoms of CHF include, but not limited to a pulmonary edema, hypoperfusion, or documented volume overload AND administration of IV diuresis or inotropic therapy, performance of aortic valvuloplasty, institution of mechanical support (IABP or ventilation for pulmonary oedema) or haemodialysis for volume overload.	2014 ACC/AHA Key Data Elements and Definitions for Cardiovascular Endpoint Events in Clinical Trials/VARC 2
Hypertension	Systolic pressure > 140 or a diastolic pressure > 90 mmHg	Sponsor
Hypotension	Systolic pressure < 90 or a diastolic pressure < 60 mmHg	Sponsor
Index hospitalization	The beginning of the Index Hospitalization is defined as the day the patient is admitted for valve implant procedure and continues until the patient is discharged from the hospital.	Sponsor
Infection	Known infection requiring intravenous antibiotics for other than prophylaxis, and/or extended hospitalization	Sponsor
Lung disease, severe	FEV1 < 50% predicted or currently on home oxygen	Sponsor
Liver disease, chronic	MELD Score ≥ 10 or Child-Pugh Class B or C	Sponsor

Term	Definition	Reference/ Justification
Mini-mental state examination (MMSE)	A questionnaire that is used extensively in clinical and research settings to measure cognitive impairment.	Pangman, VC; Sloan, J; Guse, L. (2000). "An Examination of Psychometric Properties of the Mini-Mental State Examination and the Standardized Mini-Mental State Examination: Implications for Clinical Practice". Applied Nursing Research 13 (4): 209–213.

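### When a started procedure is aborted and the valve is deployed on a later date, Day 0 moves to the later date, and non-fatal events in between fall before time zero

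*Combined protocol and SAP*

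**What the plan says.** Section 8.3 defines the start of the procedure as the first access puncture (TAVR) or the first skin incision (SAVR). It also provides: "If the valve implant is aborted (prior to or after the start of the valve implant procedure), the Day 0 visit may be re-scheduled", on condition that the patient still meets the eligibility criteria.

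For patients with more than one attempt, 11.2 states that "the last procedure with the study valve deployed will be considered the index procedure". That procedure sets both the As Treated arm and the follow-up dates. Section 11.3 continues: "The index procedure date is defined as Day 0", and "Time intervals for events will be computed by subtracting the event date minus day 0". The only fallback is narrow: "For randomized patients who do not have the procedure attempted, the randomization date will be used as Day 0".

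Appendix B fixes the hospital endpoints to the same procedure. The index hospitalization begins on what is "defined as the day the patient is admitted for valve implant procedure" and ends at discharge. A repeat hospitalization must be unplanned and must come "following discharge from the index hospitalization".

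**The concern.** These rules make time zero depend on what happened after treatment began. A patient who dies after a failed first attempt has no later procedure, so that attempt stays the index and the death counts. A patient who survives the failed attempt and is implanted on a later date gets a fresh clock, and the non-fatal complications of the first attempt fall before it. The interval between the first start and the final implant is immortal time.

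The trial is meant to establish the safety and effectiveness of the treatment strategy, and complications of a failed attempt belong to that strategy. The same clock drives the primary composite, the 30-day labeling tests in 11.5 and the 30-day and 1-year endpoints in 11.6.

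Repeat attempts are foreseeable. Section 11.3 itself allows for a severely delayed procedure. Table 8.3.2-1 has the TAVR implant aborted and delayed if intra-procedural TEE shows thrombus, which could come after access is established. For surgery, the same table contains both an abort-and-delay statement and a statement that the implant can proceed. Those two statements must be reconciled. As written, they leave open that repeat attempts differ in frequency between the arms.

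**Working it through.** **Step 1: follow one patient through the rules.** Suppose the first attempt is started and aborted, and the study valve is deployed 10 days later. Day 0 is the deployment date (11.2, 11.3). An event *k* days after the first start has time *k* − 10, which is negative for every *k* from 0 to 9.

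- Stroke, bleeding, vascular complication: negative time, so outside the 30-day and 1-year windows.
- Unplanned admission between the attempts: negative time, and also before discharge from the index hospitalization, so it cannot be a repeat hospitalization.
- First stay, if it was a separate admission: not part of the index length of stay (second labeling test in 11.5).
- Days alive and out of hospital at 1 year: 11.6 gives no start date. If counted from Day 0, the earlier hospital days drop out.
- New atrial fibrillation at the first attempt: may be treated as pre-procedural and the patient excluded, unless the CEC adjudicates it as new onset or both (first labeling test in 11.5).
- Death after the first attempt: counted, because no later procedure exists.
- Both attempts on one date: event time is 0 or later, so nothing is lost.
- Both attempts in one admission: all days stay in the index length of stay.

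The ITT sensitivity analyses do not restore these events, because randomization becomes Day 0 only when no procedure was attempted.

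**Step 2: reproduce the plan's sample size.** Inputs from 11.1: 16.6% (SAVR), 14.6% (TAVR), margin 6.0 points, one-sided 0.025, power 90%, unpooled Z test.

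n per arm = (1.960 + 1.282)² × (0.166 × 0.834 + 0.146 × 0.854) / (0.06 + 0.02)² = 10.507 × 0.263128 / 0.0064 = 432, so 864 in total.

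This matches the stated 864. The formula does not involve the time origin, so correcting Day 0 leaves it unchanged.

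**Step 3: how few lost events would matter.** The documents give no rate of aborted attempts, so this is an assumption with a range. Let *x* be the proportion of TAVR patients whose primary event is lost, with no loss in SAVR, 500 per arm (the 1000 in 11.1) and a SAVR rate of 16.6%.

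At the margin the true TAVR rate is 0.166 + 0.060 = 0.226, and the observed rate is p = 0.226 − *x*. Then:

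SE = √{[p(1 − p) + 0.166 × 0.834] / 500}, and type I error = Φ(*x*/SE − 1.960).

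For *x* = 0.005: SE = √[(0.221 × 0.779 + 0.138444)/500] = 0.02492, and Φ(0.2006 − 1.960) = 0.0393.

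For *x* = 0.010: SE = √[(0.216 × 0.784 + 0.138444)/500] = 0.02481, and Φ(0.4030 − 1.960) = 0.0597.

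The superiority column uses the same formula with a true TAVR rate of 0.166 and no true difference.

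| *x* | TAVR patients of 500 | Non-inferiority type I error | Superiority type I error |
|---|---|---|---|
| 0 | 0 | 0.0250 | 0.0250 |
| 0.0025 | 1.25 | 0.0315 | 0.0319 |
| 0.005 | 2.5 | 0.0393 | 0.0404 |
| 0.010 | 5 | 0.0597 | 0.0630 |
| 0.020 | 10 | 0.1259 | 0.1383 |

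With the maximum enrolment of 1182 (591 per arm), *x* of 0.005 and 0.010 give 0.0408 and 0.0640 for non-inferiority.

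**The case against.** The strongest reply is that the gap is narrow and that nothing is actually discarded. Adverse events are captured from randomization (9.5), the CEC adjudicates from enrollment (12.3), and 11.8.7 says all adjudicated events are analyzed. No section says that events with negative times are dropped. This is true, and it is why the repair is easy. But the analyses are rates at fixed times from Day 0, and the plan has no rule that brings an earlier event into them. Without one, the decision would be made after the events are known.

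Several limits stand. A planned return for the second implant is not an unplanned admission, so it would not count under either clock. A stroke after the first attempt arguably fails the eligibility condition for rescheduling, through exclusion 16. That narrows the stroke route, although 11.2 would still reset Day 0 for anyone who was implanted. The atrial fibrillation exclusion has the CEC exception. The rule covers both arms.

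A reader might infer that a patient readmitted months later for a second valve would also have Day 0 moved, erasing a primary event. The documents do not support this. Section 8.3 ties rescheduling to an aborted implant in a still-eligible patient, exclusion 7 bars an existing bioprosthesis, and Appendix B calls such a procedure a reintervention. What is missing is only a cross-reference in 11.2.

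A reader might also size the loss from the 0.7% aortic valve reintervention rate in Table 1.2.2-1. That figure does not count aborted attempts. Nor can lost bleeding, vascular or atrial fibrillation events be set against the 6.0-point margin, because they are not components of the primary composite.

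**Conclusion.** The point holds. For patients whose started procedure is aborted and whose valve is deployed on a later date, the stated rules place non-fatal events after the first start before time zero, and a separate first admission outside the index stay. The ITT sensitivity analyses share the defect. Atrial fibrillation from the first attempt is at risk of exclusion but not certain to be excluded.

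Size and direction are unknown. A net bias in the comparison needs unequal loss between the arms, and equal loss would largely cancel. That the rule favours TAVR is a tempting inference, but the documents give no repeat-attempt rate for either arm. The rise in one-sided type I error from 0.025 to about 0.04 to 0.06 is an illustration. It assumes that 2.5 to 5 primary-event patients of 500 are lost in the TAVR arm and none in SAVR. It shows that a handful of patients would be enough to matter, not that this many are expected. The time origin should be settled before any unblinded analysis.

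**What to change.** In 11.2 and 11.3, define Day 0 for all event, rehospitalization and hospital-day endpoints as the date of the first procedure started (first access puncture or skin incision, as 8.3 already defines it). Count events and hospital days from that date, and align the index-hospitalization definition in Appendix B with it. Use the date of the procedure with the valve deployed only for scheduling visits and echocardiograms and for the VI analyses. State in 11.2 that reinterventions as defined in Appendix B never reset Day 0.

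The cost is wording. The sample size is unaffected, and adverse events are already captured and adjudicated from randomization or enrollment. The documents do not say that the date of an aborted start is recorded, so this should be confirmed on the case report form. A few more events may count, and in these few patients the 30-day visit assessments will fall later than 30 days after the event clock starts.

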11.6 Additional Safety and Effectiveness Endpoints

The endpoints in this section will be evaluated according to the general statistical methods described in section 11.8. These endpoints will not be subject to the formal multiple comparisons correction; they are presented as part of the totality of information. All the statistical tests between the treatment arms will be two-sided tests at $\alpha=0.05$.

- Mortality (all cause & cardiovascular) at 30 days and 1 year
- Stroke (disabling and nondisabling) at 30 days and 1 year
- Death or stroke at 1 year
- Death or disabling stroke at 30 days and 1 year
- Vascular complications (major) at 30 days and 1 year
- Bleeding complications (life threatening, disabling or major) at 30 days and 1 year
- Myocardial infarction at 30 days and 1 year
- Acute kidney injury at 30 days
- Requirement for renal replacement therapy at 1 year
- New permanent pacemaker implantation resulting from new or worsened conduction disturbances at 30 days and 1 year.
- Coronary obstruction requiring intervention at 30 days and 1 year

- New York Heart Association class at 30 days and 1 year
- Hemodynamic valve performance evaluation by echocardiography for aortic valve stenosis and aortic valve regurgitation at 30 days and years 1, 2, 3, 4, 5, 7, and 10. Echo readings to be evaluated include aortic valve area, mean gradient, peak gradient, perivalvular aortic regurgitation, total aortic regurgitation, and mitral regurgitation.
- Rehospitalization (valve-related or procedure-related and including heart failure) at 30 days, 1 year and annually (up to 10 years)
- Days alive and out of hospital at 1 year
- Six-minute walk test at 30 days and 1 year
- Health status as evaluated by Quality of Life questionnaires at 30 days and 1 year
- New onset atrial fibrillation at 1 year
- ICU days and discharge location
- Structural valve deterioration at years 1-5,7 and 10

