Pulmonary hypertension	A mean pulmonary artery pressure >or equal 25 mm Hg in presence of LAP/wedge <= 15 mm Hg	ACC
Pre-existing condition	A pre-existing condition is one that is present at the start of study treatment. A preexisting condition is not an adverse event unless it worsens as a result of the study treatment.	Sponsor

Term	Definition				Reference/ Justification	
Prosthetic aortic valve stenosis criteria ^a		Normal	Mild	Moderate/severe	VARC-2	
	Quantitative Parameters (flow-dependent)^b					
	Peak velocity (m/s)	<3 m/s	3-4 m/s	>4m/s		
	Mean gradient (mmHg)	<20 mmHg	20-40 mmHg	>40 mmHg		
	Quantitative parameters (flow-independent)					
	Doppler velocity index ^c	>0.35	0.35-0.25	<0.25		
	Effective orifice area ^d	>1.1 cm ²	>1.1-0.8 cm ²	<0.8 cm ²		
	Effective orifice area ^e	>0.9 cm ²	>0.9-0.6 cm ²	<0.6 cm ²		
	^a In conditions of normal or near normal stroke volume (50–70 mL). ^b These parameters are more affected by flow, including concomitant aortic regurgitation. ^c For LVOT >2.5 cm, significant stenosis criteria is <0.20. ^d Use in setting of BSA ≥1.6 cm ² (note: dependent on the size of the valve and the size of the native annulus). ^e Use in setting of BSA <1.6 cm ² .					

Term	Definition				Reference/ Justification
Prosthetic aortic valve regurgitation criteria		Normal	Mild	Moderate/severe	VARC 2
	Semi-quantitative Parameters				
	Diastolic flow reversal in the descending aorta—PW	Absent or brief early diastolic	Intermediate	Prominent, holodiastolic	
	Circumferential extent of prosthetic valve paravalvular regurgitation (%) ^a	<10%	10-29%	≥30%	
	Quantitative parameters^b				
	Regurgitant volume (mL/beat)	<30 mL	30-59 mL	≥60 mL	
	Regurgitant fraction (%)	<30%	30-49%	≥50%	
	EROA (cm ²)	0.10 cm ²	0.10-0.29 cm ²	≥0.30 cm ²	
	
^aNot well-validated and may overestimate the severity compared with the quantitative Doppler.
 
^bFor LVOT >2.5 cm, significant stenosis criteria is <0.20.
				
	Reintervention	
Any intervention that repairs, alters or replaces a previously implanted or operated valve, which occurs after the completion of the valve implant procedure and the transfer to the procedure room. These interventions include:
 
 • Balloon aortic valvuloplasty • Surgical aortic valve replacement • Valve in valve • Paravalvular leak closure 			

Term	Definition	Reference/ Justification

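### Echoes taken after a valve has been replaced or repaired are analysed, in both arms, as performance of the valve first implanted

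*Combined protocol and SAP*

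**What the plan says.** Section 11.2 places in the Valve Implant (VI) population the treated patients "consisting of all patients who receive and retain the intended valve during the index procedure". It adds that "The VI population will be used for analysis of echo data and related endpoints", and that "Patients who receive a valve in valve implant will be part of the VI population". The only later event it names as removing a patient is conversion from TAVR to SAVR during the procedure.

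Section 11.3 governs which echoes count: "For information depending on follow-up windows any visit within the specified window will be used, without regard to the actual timing of the visit". It also says "Information dependent on a visit window, such as echo or NYHA, will be included in analysis", on the sole condition that the window opens by the analysis close date.

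Section 11.6 lists "Hemodynamic valve performance evaluation by echocardiography for aortic valve stenosis and aortic valve regurgitation" at 30 days and at years 1 to 5, 7 and 10, with two-sided tests between arms at 0.05. Section 11.7 carries the one-year methods forward to later years.

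Appendix B defines reintervention as "Any intervention that repairs, alters or replaces a previously implanted or operated valve" after the implant procedure is complete. It lists balloon valvuloplasty, surgical replacement, valve-in-valve and paravalvular leak closure. Section 11 never uses the term, and it is not an endpoint in sections 6.1 to 6.3.

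**The concern.** Ten-year echo follow-up exists to describe how the implanted valve holds up. Under these rules a patient stays in the echo set after that valve has been replaced, re-valved or repaired, and later readings describe the rescue. Where rescue improves the reading, the worst results leave the table and better ones take their place. If the arms differ in how often they are rescued, the arm with more rescues gains on gradient and regurgitation. What is at stake is the comparative durability evidence from echo, not the primary result.

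**Working it through.** **1. Figures in the plan.** The plan gives no sample size or expected rate for the echo set. Its one relevant calculation, 864 patients for 90% power, reproduces. With 432 per arm, SE = √[(0.166×0.834 + 0.146×0.854)/432] = 0.0247. The distance from the assumed difference to the margin is 0.06 + 0.02 = 0.08. Power = Φ(0.08/0.0247 − 1.96) = 0.900. The echo rule does not enter it.

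**2. Following one patient through the text.** Take a patient in either arm who keeps the assigned valve at the index procedure and has a reintervention in year 2.

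- Section 11.2: in the VI set, with no later exit.
- Section 8.3: patients who receive the assigned implant stay in the study through year 10.
- Section 8.6.4: echoes continue, here at years 3, 4, 5, 7 and 10.
- Section 11.3: each echo is used if it falls in its window and the window opens by the close date.
- Sections 11.6 and 11.7: each enters the arm summary and the between-arm test.
- Section 11.8.5: deals with missing data; there is no rule for reintervention.

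Followed as written, the year 3 to year 10 echoes of the rescue valve or repaired leak are tabulated as the original valve's performance.

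**3. A related ambiguity.** Where several procedures were attempted, 11.2 takes the last one in which the study valve was deployed as the index procedure. It does not limit this to initial implant attempts. Read literally, re-valving with a SAPIEN 3 could reset the index procedure.

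**4. Illustration with labelled assumptions.** Section 1.2.1 reports, for the earlier high-risk/inoperable cohort, 2.7% moderate paravalvular leak at 1 year (a paired echo analysis) and 0.6% surgical AVR at 1 year (Table 1.2.1-5). Assume that both apply to the same 1,000 patients, that all 6 operations were for leak, and that all 6 now read as good.

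| Rule | Calculation | Result |
|---|---|---|
| As written | 27/1000 | 2.7% |
| Stop at reintervention, nothing else | 27/994 | 2.72% |
| Count reintervened as failures | (27 + 6)/1000 | 3.3% |

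The share hidden as written is 0.6/3.3 = 18%. The second row matters: dropping post-rescue echoes alone recovers almost nothing, because it also drops the failed valves.

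For later years, hold 2.7% fixed and assume cumulative reintervention of 1%, 3%, 5% or 10%. Failure-or-reintervention becomes 3.7%, 5.7%, 7.7% or 12.7%. If one arm had 5% and the other 2%, with equal echo results, the echo table would show no difference, against 7.7% − 4.7% = 3 points.

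For mean gradient, assume a failing valve reads 40 mmHg and both rescued and untouched valves read 12. Counting failures raises the arm mean by the reintervened share × (40 − 12): 0.05 × 28 = 1.4 mmHg, or 0.15 × 28 = 4.2 mmHg. None of these gradients or later reintervention rates is in the documents. The leak and gradient examples also cannot both apply to every reintervention.

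**The case against.** **The text is silent.** No sentence says that post-reintervention echoes count, and the any-visit sentence is about timing. Section 11.8.5 also refers to an SAP for tipping-point analyses, whose text is not in the reviewed document and might contain a rule. The valve-in-valve sentence may mean only the index procedure. These cautions stand, but the reading does not rest on silence alone: 11.2 sets membership by a stated criterion fixed at the index procedure, and 11.3 gives the inclusion condition for echo by name.

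**Failures are captured elsewhere.** Structural valve deterioration is assessed through year 10 and can be determined by reoperation. Valve-related rehospitalization is analysed annually to year 10. Under 9.5, device-related and serious events are reported to year 10, and explants go for examination. So a reader who infers that rescued failures disappear from the trial goes too far. But Appendix B excludes infection and thrombosis from deterioration and ties it to changes intrinsic to the valve, so leak closure, thrombosis and infection largely fall outside it. Section 11.8.7 gives counts only for adverse events past year 1. None of this corrects the echo tables.

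**Using all data is a legitimate treatment-policy choice.** It is, if declared and labelled as the patient's haemodynamics with whatever valve is in place. The plan calls the endpoint valve performance and analyses it in patients who retained the intended valve.

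**A reader might infer that the rule favours one arm**, because 8.9 discontinues a TAVR patient given a different THV. That section concerns events after entering the procedure room and sets monitoring to Day 30 or until adverse events resolve, so it reads as an index-procedure rule. The VI rule itself treats both arms alike.

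**Conclusion.** The point holds for the echo analyses. As written, echoes after replacement, valve-in-valve, valvuloplasty or leak closure enter the year 1 to year 10 gradient, valve-area and regurgitation summaries and tests as performance of the originally implanted valve, in both arms.

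Its weight is moderate. The primary endpoint, the labeling endpoints and the sample size are unaffected, and 11.6 places the echo endpoints outside multiplicity control. The size cannot be established from the documents. The 2.7% against 3.3% contrast mixes two denominators from a high-risk cohort and assumes that every operation was for leak, which no document says. The later-year and gradient figures rest wholly on assumed rates. The direction is firmer: wherever rescue improves the reading, the table is flattered, and a between-arm distortion follows only if reintervention differs between arms. The conclusion also assumes that no rule exists in an SAP text not reviewed here.

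**What to change.** In 11.2 and 11.6, state that haemodynamic summaries and tests use echoes up to the first reintervention (Appendix B definition) or explant, in both arms. Adopt the following together with that restriction, not as optional extras:

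- the cumulative number reintervened, by arm, beside each echo time point;
- an analysis counting reintervened patients as failures, with the worst category for regurgitation and the last pre-reintervention gradient carried forward.

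Report post-reintervention echoes separately. In 11.2, limit the rule on the last procedure with the study valve deployed to initial implant attempts.

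The cost is a few sentences and some programming, with slightly fewer late echoes in the main summaries. No new visits or data are needed. The rule should be fixed before later comparative echo results are seen.
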